8.4.4 Calculation or derivation of pharmacokinetic variables

Summary statistics of the PK will be generated for each visit where serum samples are collected. In addition, estimation of PK parameters, ie, C_{max} , t_{max} , and $AUC_{[0,28d]}$ will be computed for the first dosing cycle using noncompartmental estimation method. C_{max} and T_{max} are direct measurements of the maximum observed concentration and the time to reach the C_{max} respectively during the first dosing cycle.

8.4.5 Calculation or derivation of immunogenicity variables

Assessments of anti-drug antibodies (ADA) will be conducted using a tiered approach (screen, confirm, titer). The presence of in vitro neutralizing antibody (nAb) activity will be tested in all ADA-positive samples time points using a ligand binding assay.

8.5 Methods for statistical analyses

Demographics and subject characteristics will be summarized by treatment group using frequency and percentages (for categorical variables) and descriptive statistics of mean, standard deviation, minimum, median and maximum (for continuous variables) using the full analysis set.

The analysis of the primary and secondary endpoints will include all data captured during the 84-day treatment period, including follow-up (where applicable), unless the patient withdraws consent to study participation, regardless of whether study treatment was prematurely discontinued, or delayed, and/or irrespective of protocol adherence. To emphasize the importance of collecting complete primary and secondary outcome data in all patients, the informed consent form (ICF) form will ask that patients continue study assessments for the whole 84-day double-blind treatment period, including follow-up, even if they discontinue study treatment prematurely.

Descriptive statistics will also be provided for safety and efficacy data. Unless otherwise stated, the data analysis include subjects in the full analysis set. Descriptive statistics on continuous variables will be summarized by treatment group using mean, standard deviation, minimum, median and maximum, while categorical data were summarized using frequency counts and percentages. When data are summarized by time, the values recorded against the scheduled time points listed in the protocol will be used. When assessing minimum/maximum increases or decreases during the study, all assessments, including unscheduled assessments will be used. For analysis assessing change from baseline, only subjects with both baseline and at least 1 evaluable post-baseline measure will be included.

Given there is a single primary endpoint and treatment comparison no formal testing strategy will be used for the analysis in this study.

The prior medications, categorized according to the WHO Drug Reference List dictionary which employs the Anatomical Therapeutic Chemical (ATC) classification system, will be summarized by treatment group as frequency and percentage of subjects reporting usage.

The concomitant medication will be categorized according to the WHO Drug Reference List dictionary which employs the Anatomical Therapeutic Chemical (ATC) classification system. The frequency and percentage of subjects taking concomitant medications and non-drug therapies during the treatment period will be summarized by drug class and drug name using ATC code.

8.5.1 Analysis of the primary variable(s)

The change from baseline in pre-BD FEV₁ up until the EOT at Visit 10 will be compared between the 30 mg benralizumab group and placebo using a repeated measures analysis on patients with a baseline pre-BD FEV₁ and at least 1 post-randomization pre-BD FEV₁ in the full analysis set. The dependent variable will be the change from baseline in pre-BD FEV₁ at post-baseline protocol specific visits (up to and including the EOT Visit). Treatment group will be fitted as the explanatory variable, region, visit and treatment*visit interaction as fixed

effects and baseline pre-bronchodilator FEV₁ as a covariate. The variance-covariance matrix will be assumed to be unstructured. If the procedure does not converge then a compound symmetric variance-covariance matrix will be used instead. The model is:

$$\text{Change in FEV}_1 = \text{Treatment group} + \text{baseline pre-BD FEV}_1 + \text{region} + \text{visit} + \text{treatment} * \text{visit}$$

The primary objective of the study is to determine the effect of Benralizumab on the time course of change (onset and maintenance of effect) of pre-BD FEV₁ using the model described above. The first post baseline timepoint where the p-value for the mean difference between benralizumab and placebo is less than or equal to 0.05 will be used to determine time to onset of effect. The average over the mean differences between benralizumab and placebo based on the change from baseline (Visit 4) to Days 28 (Visit 8), 56 (Visit 9) and 84 (Visit 10) in pre-BD FEV₁ will be used to determine if the study is positive as well as maintenance of effect. Contrasts will be used to obtain estimates of the treatment differences over Days 28, 56 and 84 as well as at each timepoint separately.

Additional supportive analyses to the primary objective of the study will be carried out as detailed below.

The modelled treatment response as well as differences between benralizumab and placebo using the mean change from baseline in pre-BD FEV₁ endpoint using an exponential model over time will be estimated. The model will be used to determine the modelled time to onset of effect where the pre-BD FEV₁ reaches thresholds for improvement in both mean differences between benralizumab and placebo as well as within treatment change from baseline differences. If the exponential model does not fit the time profile alternative models will be assessed.

The first timepoint using the repeated measures analyses where the observed mean treatment difference between benralizumab and placebo is first greater than different thresholds for improvement will also be presented. In addition for each treatment group time to event analyses will be carried out to present the proportion of patients with onset of effect over time using different within patient change from baseline thresholds.

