8.4.1.1 Pre-bronchodilator forced expiratory volume in 1 second

Time to onset of effect in Pre-BD FEV₁ is the primary objective of this study. The mean change from baseline to each of the post-randomization visits (post Visit 4) up to and including the end of double-blind treatment visit at day 84 (Visit 10) of pre-BD FEV₁ will be the primary efficacy variable of this study.

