8.5.2 Analysis of the secondary variable(s)

8.5.2.1 Analysis methods for secondary efficacy variables

Secondary efficacy variables in this study include:

- Absolute and percentage change from baseline of peripheral blood eosinophil counts until EOT at Visit 10
- Change from baseline in FVC until EOT at Visit 10
- Change from baseline in ACQ-6 score until EOT at Visit 10
- Change from baseline in SGRQ score until EOT at Visit 10

- Change from baseline in FeNO (ppb) until EOT at Visit 10

For each variable, the objective is to determine the effect of benralizumab on the time course of change (onset and maintenance of effect).

Other variables include:

- Change from baseline in Patient Global Impression of Severity until EOT at Visit 10
- Patient and Clinical Global Impression of Change until EOT at Visit 10

For the following variables:

- Peripheral blood eosinophil counts
- Exhaled nitric oxide (FeNO)
- FVC
- ACQ-6 score
- SGRQ
- Change from baseline in PGI-S as a continuous measure.

The change from baseline at each timepoint will be compared between benralizumab and placebo using a repeated measures analysis. The dependent variable will be change from baseline for each endpoint. Treatment group will be fitted as the explanatory variable, region, visit and treatment*visit interaction as fixed effects and corresponding baseline as a covariate. The variance-covariance matrix will be assumed to be unstructured. If the procedure does not converge the compound symmetric variance-covariance matrix will be used instead. The least squares mean for the difference in treatment groups using the interaction between visit and treatment group its 95% CI, and the 2-sided p-values will be reported for each post baseline visit.

As for the primary endpoint the first post baseline timepoint where the p-value for the mean difference between benralizumab and placebo is less than or equal to 0.05 from the repeated measures analysis will be used to determine time to onset of effect. The average over the mean differences between benralizumab and placebo based on the change from baseline (Visit 4) to Days 28 (Visit 8), 56 (Visit 9) and 84 (Visit 10) will be used to determine maintenance of effect. Contrasts will be used to obtain estimates of the average treatment differences over Days 28, 56 and 84 as well as for each timepoint separately.

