## **4. ANALYSIS METHODS**

### **4.1 General principles**

The analysis of the primary and secondary efficacy endpoints will include all data captured during the 12-week double-blind treatment period, defined as the period after administration of randomized IP at Visit 4 (Week 0) and the conclusion of Visit 10 (Week 12), inclusive. This includes data regardless of whether study treatment was prematurely discontinued or delayed, and/or irrespective of protocol adherence, unless the patient withdraws consent to study participation. The statistical analyses will compare benralizumab with placebo. The analysis of safety endpoints will include all data captured during the on-study period, defined as the period after first administration of randomized IP at Visit 4 (Week 0) and the conclusion of the scheduled post-treatment FU visit (Week 11), inclusive.

The data analyses will be conducted using the SAS® System 9.2 (SAS Institute Inc., Cary, NC) or higher version. Pharmacokinetic analyses will be performed using WinNonlin (version 6.3, or higher, Certara, L.P., St. Louis, MO).

Summary data will be presented in tabular format by treatment group. Descriptive statistics on continuous variables will be summarized by treatment group using mean, standard deviation, median, quartile, and range as applicable, while categorical data will be summarized using frequency counts and percentages. When data are summarized by time, the values recorded against the scheduled timepoints listed in the protocol will be used. When assessing minimum/maximum increases or decreases during the study, all assessments, including unscheduled assessments will be used. For analysis assessing change from baseline, only patients with both baseline and at least 1 evaluable post-baseline measure will be included.

Given there is a single primary endpoint and treatment comparison, no formal testing strategy will be used for the analysis in this study.

All hypothesis testing will be reported using 2-sided tests. All p-values apart from the primary analyses of the primary endpoint will be nominal. All p-values will be rounded to 4 decimal places.

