#### **4.2.5 Primary outcome variable**

##### **4.2.5.1 Primary analysis**

The change from baseline in pre-BD FEV1 up until the EOT at Visit 10 will be compared between the 30 mg benralizumab group and placebo using a mixed-effect model for repeated measures (MMRM) analysis on patients with a baseline pre-BD FEV1 and at least 1 post-randomization pre-BD FEV1 in the FAS.

The dependent variable will be the change from baseline in pre-BD FEV1 at post-baseline protocol specific visits (up to and including the EOT Visit). Treatment group will be fitted as the explanatory variable, region, visit and treatment\*visit interaction as fixed effects, and baseline pre-BD FEV1 will be fitted as a covariate. The variance-covariance matrix will be assumed to be unstructured. If the procedure does not converge, then a compound symmetric variance-covariance matrix will be used instead. The model is:

$$\text{Change in FEV}_1 = \text{treatment} + \text{baseline pre-BD FEV}_1 + \text{region} + \text{visit} + \text{treatment} * \text{visit}$$

The primary objective of the study is to determine the effect of benralizumab on the time course of change (onset and maintenance of effect) of pre-BD FEV1 using the model described above. The first post-baseline timepoint where the p-value for the mean difference between benralizumab and placebo is  $\leq 0.05$  will be used to determine time to onset of effect. The average over the mean differences between benralizumab and placebo based on the change from baseline (Visit 4) to Days 28 (Visit 8), 56 (Visit 9), and 84 (Visit 10) in pre-BD FEV1 will be used to determine if the study is positive as well as to determine the

maintenance of effect. Contrasts will be used to obtain estimates of the treatment differences over Days 28, 56, and 84, as well as at each timepoint separately.

Results will be presented in terms of least square means (LSMEANS), treatment differences in LSMEANS, 95% confidence intervals (CI) of treatment differences, and p-values at each planned timepoint.

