## **4.2.6 Secondary efficacy outcome variables**

### **4.2.6.1 Secondary analyses**

For each secondary efficacy variable described in Section 3.2, the objective is to determine the effect of benralizumab on the time course of change (onset and maintenance of effect).

FEV1 responder at each post-baseline visit will be defined as a subject with change from baseline  $\geq$  prespecified cutoffs as in Section 3.1, and analysed using a logistic regression model with repeated measures using generalized equation estimate method. The model will include treatment, region, visit and treatment group by visit interaction as fixed factors, and baseline FEV1 scores as a covariate. The variance-covariance matrix will be assumed to be unstructured.

The percent change from baseline at each timepoint for the eosinophils counts, change from baseline at each timepoint for Pre-BD FVC, ACQ-6 score, SGRQ score, and FeNO will be compared between benralizumab and placebo using an MMRM analysis described in the primary analysis above. The least squares mean for the difference in treatment groups using the interaction between visit and treatment group, its 95% CI, and the 2-sided p-values will be reported for each post-baseline visit.

As for the primary endpoint, the first post-baseline timepoint where the p-value for the mean difference between benralizumab and placebo is less than or equal to 0.05 from the repeated measures analysis will be used to determine time to onset of effect for each secondary parameter. The average over the mean differences between benralizumab and placebo based on the change from baseline (Visit 4) to Days 28 (Visit 8), 56 (Visit 9), and 84 (Visit 10) will be used to determine maintenance of effect. Contrasts will be used to obtain estimates of the average treatment differences over Days 28, 56, and 84.

Results will be presented in terms of LSMEANS, treatment differences in LSMEANS, 95% CIs of treatment differences, and p-values at each planned timepoint. To explore correlations between changes in eosinophil depletion and lung function, and correlations between changes in FeNO and lung function, the following analyses will be conducted, blood eosinophil data collected at Screening visit will be used in the analyses below to be consistent with the subgroup analysis of pre-BD FEV1 by baseline EOS categories:

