- Analyses will be conducted on change from baseline versus baseline eosinophil count at Day 28 and Day 84 in pre-BD FEV1 using a moving average and MMRM approach. In this analysis, patients will be ordered by baseline eosinophil count and grouped by percentile into overlapping subgroups (0 – 40th, 10th – 50th, 20th – 60th, 30th – 70th, 40th – 80th, 50th - 90th, 60th – 100th). The MMRM model will be then applied to each subgroup to estimate the treatment difference at Day 28 and Day 84 separately and associated 95% CI for each percentile grouping.
- A scatterplot of observed change in pre-BD FEV1 at Day 28 and 84 versus baseline eosinophils at Day 28 and Day 84 will be prepared separately with locally weighted scatter plot smoothing curves (LOESS) and corresponding 95% CIs superimposed.
- Same kinds of MMRM and LOESS analyses will be performed using baseline FeNO data.
- If significant treatment effect is detected at timepoints earlier than Day 28, the same kinds of MMRM and LOESS analyses will also be performed at the earliest timepoint where significant treatment effect is detected.

A scatter plot with correlation coefficient will be provided for baseline FeNO and EOS count data to evaluate the association between baseline FeNO and EOS.

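### Onset is named at the first of six unadjusted visit tests, in either direction and without regard to the Day 28/56/84 average, so an onset day can be reported in a negative trial

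*Protocol*

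**What the plan says.** Onset is central to this trial: it is in the title, and Protocol 8.4.1.1 states "Time to onset of effect in Pre-BD FEV₁ is the primary objective of this study". Protocol 2.1 and SAP 1.1.1 put both onset and maintenance under the primary objective.

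Two decision rules come from one repeated measures model:

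- **Study success and maintenance:** the average treatment difference over Days 28, 56 and 84.
- **Onset:** in Protocol 8.5.1, "The first post baseline timepoint where the p-value for the mean difference between benralizumab and placebo is less than or equal to 0.05". SAP 4.2.5.1 repeats it: "The first post-baseline timepoint where the p-value for the mean difference between benralizumab and placebo is" at or below 0.05.

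SAP 4.2.5.4 lists the post-baseline FEV₁ visits up to end of treatment as Days 3, 7, 14, 28, 56 and 84. SAP 4.1 makes all tests two-sided.

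On multiplicity, SAP 4.1 says "Given there is a single primary endpoint and treatment comparison, no formal testing strategy will be used for the analysis in this study", and Protocol 8.5 says the same. SAP 4.1 adds: "All p-values apart from the primary analyses of the primary endpoint will be nominal".

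The onset rule is reused for the secondary variables. In Protocol 8.5.2.1 the first visit at that p-value "from the repeated measures analysis will be used to determine time to onset of effect"; in SAP 4.2.6.1 it "will be used to determine time to onset of effect for each secondary parameter". SAP 4.2.6.1 also plans further eosinophil and FeNO analyses at the earliest significant visit: "If significant treatment effect is detected at timepoints earlier than Day 28".

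**The concern.** Three things are missing from the onset rule.

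1. **Direction.** A visit at which placebo is significantly better satisfies the rule as written.
2. **A link to study success.** Neither document makes onset conditional on the Day 28/56/84 average, so a negative trial can still yield an onset day.
3. **Any allowance for searching six visits.** The reason given for having no testing strategy, one endpoint and one comparison, fits the average contrast. It does not fit a search for the first significant visit.

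The status of the per-visit p-values is also unsettled. The rule stands in the SAP section headed as the primary analysis, which suggests that they fall under the exception to nominal status. Yet Protocol 2.2 and SAP 1.1.2 list per-visit FEV₁ change as a secondary outcome.

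Because the rule takes the first significant visit, a chance result at Day 3, 7 or 14 settles the answer whatever follows. The consequence is a misleading answer to the trial's named question, repeated for each secondary variable and carried into the analyses triggered at an early significant visit.

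**Working it through.** **Inputs** (Protocol 8.2, SAP 1.3): 115 per arm, SD 375 mL, within-subject correlation 0.6, two-sided alpha 0.05, average difference 138 mL (or 120 mL). The documents give 0.6 when sizing the three-visit average. Applying it equally to all six visits is an assumption, so a range is shown. No dropout was applied.

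**Reproducing the plan's power**

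- Per-visit standard error: 375 × √(2/115) = 49.45 mL.
- Standard error of the three-visit average: 49.45 × √((1 + 2 × 0.6)/3) = 42.35 mL.
- Power at 138 mL: 138/42.35 = 3.26, and Φ(3.26 − 1.96) ≈ 90.3%. The plan says about 90%.
- Power at 120 mL: 80.9%. The plan says about 80%.

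**Reference for six tests:** if the visits were independent, 1 − 0.95⁶ = 26.5%. Correlation lowers this, so the six visit z-statistics were simulated as multivariate normal (2 million trials per scenario; 1 million for the decaying-correlation case). Each simulated trial recorded the first visit with |z| ≥ 1.96, its sign, and the result for the average.

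**Results at correlation 0.6**

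| Scenario and outcome | Rule as written | Favourable visits only | Favourable visits, and average significant in favour |
|---|---|---|---|
| No effect: an onset day is named | 18.7% | 9.3% | 2.4% |
| No effect: onset day named and average not significant | 13.8% | 6.9% | 0 by construction |
| 0 through Day 14, 138 mL from Day 28: earlier day named | 11.8% | 5.9% | 5.9% |
| Constant 138 mL from Day 3: Day 3 named | 79.7% | 79.7% | 76.8% |
| Constant 138 mL from Day 3: no onset named | 3.0% | 3.0% | 9.8% |

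The Day 3 entry can be checked by hand: 138/49.45 = 2.79, and Φ(2.79 − 1.96) ≈ 79.7%. The 2.4% cannot exceed 2.5%, because every onset claim then needs the average to be significant in one direction.

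**Sensitivity of the rule as written**

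- No effect: 22.5% to 13.9% for correlations 0.4 to 0.8.
- Effect from Day 28, earlier day named: 13.1% to 9.8% over the same range.
- Correlation decaying with visit order (0.6 between neighbours): 21.9% and 12.3%. Under the combined rule these become 2.4% and 6.0%.

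**The case against.** The best reply is that the plan already reserves its only confirmatory claim for the average. Protocol 2.2 and SAP 1.1.2 list FEV₁ change at all clinic visits as secondary, so on a natural reading the visit tests are nominal. The rule concerns an effect of benralizumab, the supportive onset analyses use thresholds for improvement, and SAP 4.2.5.1 reports every visit's estimate and confidence interval. A placebo-favouring onset would be noticed, and reading direction into the rule halves the false-onset figure to 9.3%.

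On the remedy, conditioning on the average does nothing for a too-early day: the whole fall from 11.8% to 5.9% comes from the direction requirement. The condition also carries the cost in missed onset days. The extra analyses in SAP 4.2.6.1 are introduced as exploratory. Finally, no effect before Day 28 is an assumed profile; Protocol 1.1 describes blood eosinophil depletion within 24 hours.

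Much of this is fair. The success test is sound, the Day 28 profile is only illustrative, and the too-early gain does belong to the direction requirement. But the onset rule is part of the primary outcome measure in Protocol 2.1 and SAP 1.1.1, so the secondary listing does not settle the status of its p-values. The threshold and Bayesian analyses are labelled supportive; they neither replace nor restrict the p-value rule. With direction assumed, false onset is still 9.3%, and 6.9% of trials of an ineffective drug would name an onset day beside a non-significant average. Only the condition on the average removes those.

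**Conclusion.** The concern holds. Followed literally, the rule can name an onset day in a negative trial, or from a visit that favours placebo. With no effect this happens in 18.7% of trials (13.9% to 22.5% over correlations 0.8 to 0.4), half of them favouring placebo. In 13.8% the average is also not significant. If the effect is zero through Day 14 and 138 mL from Day 28, a day that is too early is named in 11.8%.

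These figures rest on the plan's SD and sample size, normality, complete data, and one correlation across all visits. The success decision is a single contrast at two-sided 0.05 and is not inflated. This should be fixed, because the affected rule answers the question the trial is named for.

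**What to change.** In Protocol 8.5.1 and SAP 4.2.5.1:

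1. Determine onset only if the Day 28/56/84 average is significant in favour of benralizumab; otherwise report *onset not determined*.
2. Count a visit only if p ≤ 0.05 and the difference favours benralizumab.
3. State that the per-visit p-values are nominal.

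Apply (1) and (2) to the secondary variables in Protocol 8.5.2.1 and SAP 4.2.6.1, using each variable's own average and its own direction of improvement.

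This needs no patients and no alpha, and leaves the success test unchanged. It is wording only, although a substantial protocol change would go through the amendment procedure in Protocol 10.5. The statistical cost under a constant effect from Day 3 is:

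- **138 mL:** Day 3 is named in 76.8% of trials instead of 79.7%, and no onset is named in 9.8% instead of 3.0%.
- **120 mL:** 63.2% instead of 68.0%, and 19.3% instead of 7.3%.

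Nearly all trials left without an onset day are those whose average is not significant (100 − 90.3 = 9.7% of trials at 138 mL).

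The fix does not fully protect the day itself: 5.9% too-early onset remains in the Day 28 scenario. Testing backward from Day 28 would lower that to 2.5%, but Day 3 would then be named in only 58% of trials with a constant 138 mL effect. That is an option, not part of the request.

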1.2 Rationale for study design, doses and control groups

This is a randomized, double blind, placebo controlled global study designed to investigate the onset of effect of benralizumab (30 mg) administered subcutaneously (SC) on lung function in severe asthmatics still uncontrolled on standard of care therapy(-ies). Three doses will be given every 4 weeks on Day 0, Day 28 (± 3 days) and Day 56 (± 3 days).

The dose chosen, 30 mg SC, is based on all available efficacy and safety data, as well as population exposure-response modelling and stochastic simulations from earlier benralizumab trials.

A 12 week treatment duration, with 3 doses of benralizumab given every 4 weeks, will characterize the full time course of effect of benralizumab on lung function profiling the effect on FEV₁ from onset to the estimated plateau of effect at 12 weeks, as observed in the Ph2b study.

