2.2 Secondary objectives

Secondary objectives	Outcome measure
To determine time course of effect of benralizumab on blood eosinophils and correlate changes in eosinophil depletion with lung function	Change from baseline in blood eosinophils (from hematology) to end of treatment together with the correlation with lung function
To determine the effect of benralizumab on the time course of change and maintenance on lung function.	Change from baseline (Visit 4) in pre-BD FEV ₁ at all clinic visits compared to placebo Change from baseline (Visit 4) in pre-BD forced vital capacity (FVC) at all clinic visits compared to placebo
To determine the time course of the effect of benralizumab on asthma control metrics	Change from baseline (Visit 4) in Asthma Control Questionnaire-6 (ACQ-6) score at all post-baseline assessment timepoints
To determine the time course of effect of benralizumab on health related quality of life	Change from baseline (Visit 4) in St. George's Respiratory Questionnaire (SGRQ) score at all post-baseline assessment timepoints
To determine the effect of benralizumab on the time course of change in exhaled nitric oxide (FeNO)	Change from baseline in FeNO (ppb) compared to placebo to end of treatment (Visit 10)

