8.2 Sample size estimate

The study is powered for the primary objective of the study to determine the effect of benralizumab on the time course of change (onset and maintenance of effect) of pre-BD FEV₁. The first post baseline timepoint where the p-value for the mean difference between benralizumab and placebo is less than or equal to 0.05 will be used to determine time to onset of effect. The average over the mean differences between benralizumab and placebo based on the change from baseline (Visit 4) to Days 28 (Visit 8), 56 (Visit 9) and 84 (Visit 10) in pre-BD FEV₁ will be used to determine if the study is positive as well as maintenance of effect.

The benralizumab Phase 2b study MI-CP220 ([Castro et al 2014](#)) as well as results from the benralizumab Phase 3 asthma exacerbation studies were used as a basis for the sample sizing. From these studies, it is expected that around 115 patients per treatment arm (230 in total) will provide approximately 90% power for the primary endpoint pre-BD FEV₁ with type I error controlled at a two-sided alpha level of 0.05 if the true average over the mean treatment differences (benralizumab – placebo) across Days 28 (Visit 8), 56 (Visit 9) and 84 (Visit 10) is 138 mL. The sample size will also be sufficient to have approximately 80% power for an average over the mean treatment difference of 120 mL. The assumed variability has a within group standard deviation of 375 mL and within subject correlation of 0.6. If the within

subject variability is reduced to 350 mL the sample size would be sufficient to have 80% power for an average of 110 mL. In addition, it is expected that around 115 patients per treatment arm will have 80% power to detect a true treatment difference (benralizumab – placebo) of 130 mL assuming a within-group standard deviation of 350 ml or a true treatment difference of 140 mL assuming a standard deviation of 375 mL. Based on these assumptions, the minimum difference that would be statistically significant at the 0.05 level range from approximately 85 to 100 mL. The sample size was estimated using nQuery+nTerim version 3.0 using methodology in (Liu et al 2005)

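### Maintenance of effect is judged by the Day 28/56/84 average with no condition on Day 84, so an effect lost by Day 84 could still be called maintained

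*Protocol*

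**What the plan says.** Protocol 8.5.1 states that the average of the Day 28, 56 and 84 differences in change from baseline in pre-bronchodilator FEV1 "will be used to determine if the study is positive as well as maintenance of effect". SAP 4.2.5.1 repeats this: the average "will be used to determine if the study is positive as well as to determine the" maintenance of effect. The protocol synopsis, Protocol 2.1 and 8.2, and SAP 1.1.1 and 1.3 give the average the same double role.

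For the secondary variables, SAP 4.2.6.1 says that the same average "will be used to determine maintenance of effect", and Protocol 8.5.2.1 agrees.

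Visit-wise results are also planned. Protocol 8.5.1: "Contrasts will be used to obtain estimates of the treatment differences over Days 28, 56 and 84 as well as at each timepoint separately". SAP 4.2.5.1 promises "treatment differences in LSMEANS, 95% confidence intervals (CI) of treatment differences, and p-values at each planned timepoint". One secondary objective also names maintenance, "To determine the effect of benralizumab on the time course of change and maintenance on lung function" (Protocol 2.2), with FEV1 change at all clinic visits as an outcome.

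Neither document sets a Day 84 condition, a trend contrast or a retention threshold for maintenance.

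**The concern.** Maintenance is a statement about order in time: the effect appeared and was still there later. The average of three visits carries no order. True differences of 138/138/138 mL, 276/138/0 mL and 0/138/276 mL at Days 28/56/84 all average 138 mL and give the same test result. For FEV1, a maintenance conclusion drawn from this average therefore adds nothing to the finding that the study is positive.

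A significant average shows a mean benefit over Days 28 to 84. It does not show that the benefit was present at the end of treatment. The stated rule can thus give a wrong answer to one of the two named parts of the primary objective, and the same holds for every secondary variable judged in this way.

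**Working it through.** **Inputs** (Protocol 8.2, SAP 1.3): 115 per arm; within-group SD 375 mL; within-subject correlation 0.6; three visits; "type I error controlled at a two-sided alpha level of 0.05"; design effects for the average of 138 mL and 120 mL. No dropout rate is given, so none is applied. Equal correlation between visits and a normal approximation are used.

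**Standard errors of the treatment difference**
- Single visit: 375 × √(2/115) = 49.5 mL; smallest significant difference 1.96 × 49.5 ≈ 97 mL.
- Average of three visits: 49.5 × √((1 + 2 × 0.6)/3) = 42.3 mL; smallest significant difference 1.96 × 42.3 ≈ 83 mL.
- Day 84 minus Day 28: 49.5 × √(2 × (1 − 0.6)) = 44.2 mL.

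**The plan's own figures reproduce.** Power is Φ(effect/SE − 1.96). For 138 mL: 138/42.3 = 3.26, giving 90.3% (stated: approximately 90%). For 120 mL: 120/42.3 = 2.83, giving 80.9% (stated: approximately 80%). The stated range of about 85 to 100 mL for the smallest significant difference is close to the 83 and 97 mL above.

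**Chance that the average is significant when the true Day 84 difference is nil.** Here *maintained* is read as the average being significant in favour of benralizumab. The same formula is used, with the mean of the three true differences as the effect.

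| True differences, Days 28/56/84 (mL) | Mean (mL) | Mean/SE | Average significant |
|---|---|---|---|
| 138/0/0 | 46 | 1.09 | 19% |
| 138/69/0 | 69 | 1.63 | 37% |
| 138/138/0 | 92 | 2.17 | 58% |
| 200/100/0 | 100 | 2.36 | 66% |
| 207/207/0 or 276/138/0 | 138 | 3.26 | 90% |

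For 138/138/0 the figure runs from about 51% to 73% over correlations of 0.4 to 0.8 and SDs of 350 to 375 mL.

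**Adding a Day 84 condition.** The three differences were simulated as trivariate normal, with 1,000,000 draws per profile. Requiring Day 84 to be significant in favour of benralizumab as well cuts the chance to about 2.5% in every row of the table.

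**Cost when the effect truly holds**

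| Constant effect (mL) | Average alone | Day 84 alone | Both |
|---|---|---|---|
| 138 | 90% | 80% | 78% |
| 120 | 81% | 68% | 66% |

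**The case against.** **A lost effect would be visible.** The Day 84 difference will be reported with its CI and p-value, FEV1 responders are analysed at each visit, and a secondary objective covers the time course. This stands: a reader of the study report would see a nil Day 84 result. But none of these outputs is tied to the maintenance conclusion, and SAP 4.1 calls all p-values outside the primary analyses of the primary endpoint nominal.

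**No pass/fail rule is written.** The average is to be used to determine maintenance, without a threshold. This also stands. Reading maintenance as a significant average is an assumption, and the missing threshold is part of the gap.

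**The fade profiles are hypothetical.** This stands too. A reader might infer that a vanished effect *would* be declared maintained. The documents do not support that: the chance depends on the earlier effects. The 90% figure needs about 207 mL at both earlier visits, or 276 mL at Day 28, which is twice the 138 mL design average.

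**The expected plateau.** A reader might argue that, because the protocol expects a course "from onset to the estimated plateau of effect at 12 weeks, as observed in the Ph2b study", Days 28 and 56 cannot speak to maintenance. This adds little. The objective concerns maintenance of effect, not of a plateau, and if Day 84 is the only plateau visit, a Day 84 test cannot show that a plateau held either.

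**A Day 84 test is imperfect.** It shows presence, not retention: a true profile of 276/207/138 mL, where the effect halves, still meets both conditions about 80% of the time. Conversely, a non-significant Day 84 result does not prove loss. The Day 84 minus Day 28 change should therefore be reported as well.

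**Conclusion.** The concern holds in a limited form. The Day 28/56/84 average is the only criterion named for maintenance, for FEV1 it is the same contrast that decides positivity, and it cannot tell a held effect from a lost one. With a nil true Day 84 effect, the chance of a significant average runs from about 19% to about 90% over the profiles shown. These figures rest on the plan's SD, correlation and sample size, on assumed fade profiles, on no dropout, and on reading maintenance as a significant average.

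A reader might go further and infer that the study's main result is compromised. It is not: the test of positivity, its type I error, the sample size and the data collection are unaffected. This should be fixed, but it is a gap in how one conclusion is defined and not a flaw in the primary test.

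**What to change.** Keep the Day 28/56/84 average as the sole test of whether the study is positive. For maintenance, state in Protocol 8.5.1 and SAP 4.2.5.1:

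*Maintenance of effect is concluded only if the Day 28/56/84 average is significant in favour of benralizumab and the Day 84 LS mean difference from the same MMRM favours benralizumab with its 95% CI excluding 0.*

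Report the Day 84 minus Day 28 change in treatment difference with its 95% CI (SE about 44 mL on the plan's inputs), and say that a non-significant Day 84 difference is not by itself evidence of loss.

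Align the wording in the protocol synopsis (objectives and statistical methods), Protocol 2.1, 8.2 and 8.5.2.1, and SAP 1.1.1, 1.3 and 4.2.6.1, so that no section still derives maintenance from the average alone.

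**Cost:** changes of wording and one extra contrast from a model already fitted, with no new data. Power for positivity is unchanged. The maintenance claim becomes harder to reach under a constant effect: about 78% instead of 90% at 138 mL, and about 66% instead of 81% at 120 mL.
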